6.5.4.2.3. Pain

The management of pain should be done according to severity and recommended drugs as per institutional guidelines. Please, review Table 6-5 before using concomitant medications.

7. STUDY INTERVENTION DISCONTINUATION, END OF STUDY AND EARLY STUDY TERMINATION

7.1. Study Intervention Discontinuation

Study treatments (i.e., xevinapant/matched placebo, cisplatin/carboplatin and IMRT) must be discontinued under the following circumstances:

- Disease progression, including clinical progression as judged by the Investigator, treatment failure, local or distant relapse, second cancers, or start of any new anticancer treatment including salvage surgery (see EFS definition in Table 3-1 for further details).
- Participant withdrawal of consent for treatment.
 - Participants may voluntarily withdraw consent at any time. If such withdrawal occurs, every effort should be made by the Investigator to determine the primary/underlying reason for this decision, which should be recorded in the EOT eCRF. The participant should be encouraged to remain on study to be followed for survival and/or efficacy assessments.
- Unacceptable toxicity/AEs, that result in a significant risk to the participant's safety.
 Participants who are removed from study treatment due to AEs are to be treated and followed up for these AEs according to standard medical practices.

- Any protocol deviation that results in a significant risk to the participant's safety.
- · Pregnancy.
- Investigator decision in the participant's best interest.
 - The primary reason for this decision (e.g., lack of efficacy, AE) must be recorded in the eCRF.
- Early study termination by the Sponsor, Steering Committee, the Investigator, the IEC/IRB or the Regulatory Agencies (Section 7.4).

7.2. End of Study

The EOS will be triggered once 386 OS events are observed or the last on-study participant has reached his/her 60-months post-randomization visit. At this timepoint (± 2 months), all participants who have not previously discontinued from the study prematurely will undergo the EOS assessments and will be considered as having completed the study.

7.3. Premature Study Withdrawal (Participant Level)

Premature withdrawal from the study can be triggered by:

- Participant withdrawal of consent for study participation.
 - Participants may voluntarily withdraw consent at any time. If such withdrawal occurs, every effort should be made by the Investigator to determine the primary/underlying reason for this decision and that should be recorded as reason in the End of Study eCRF i.e., if the underlying reason for the decision is toxicity (e.g., AE) this should be recorded as such and the Investigator has to follow up the participant until the AE or SAE is resolved.
- At the discretion of the Investigator for safety, behavioral, compliance, or administrative reasons (e.g., disruption of operations due to natural disasters, interruption of laboratory or facility accreditation, participant moving to another country, resignation of key staff).
 - The primary reason for this decision must be recorded in the CRF.
- Participant lost to follow-up (Section 7.5).
- Death.
- Early study termination by the Sponsor, Steering Committee, the Investigator, the IEC/IRB or the Regulatory Agencies (Section 7.4).

Should a participant be withdrawn from the study, EOS assessments should be performed prior to any further therapeutic intervention whenever possible. Results of these assessments are to be recorded in the eCRF, together with a description of the reasons for study discontinuation.

7.4. Early Study Termination by the Sponsor, Steering Committee, the Investigator, the IEC/IRB or the Regulatory Agencies

The study may be prematurely terminated by the Sponsor, Steering Committee, the Investigator, the IEC/IRB or the Regulatory Agencies at any time, for the following reasons:

- Medical or ethical reasons impacting the continuation of the study.
- Difficulties in recruiting participants.
- Ineffectiveness of the study medication.
- Onset of adverse reactions of investigational drug that are unacceptable and unknown to date with regards to their nature, severity and duration; or an unexpected incidence of any unacceptable adverse reaction.
- Business reasons.

If the study is prematurely terminated, the Investigator must promptly inform the study participants and ensure that they receive appropriate therapy and follow-up. All assessments described in Section 7.1 for premature withdrawal of the participant should be followed. The Investigator may be informed of additional procedures to be followed in order to ensure that adequate consideration is given to the protection of the participant's interests.

The Investigator will be responsible for informing the IRB and/or IEC of the early termination of the study. If the IEC/IRB terminates the study or suspends its approval, the Investigator should promptly inform the Sponsor and provide a detailed written explanation of the termination.

Please refer to Section 7.3 for study discontinuation at the participant level.

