MS202359 0006 **Participant** Participants will be followed up until premature discontinuation from study or until the last on-study participant duration reaches his/her 60-months post-randomization visit, whichever occurs first. **Statistical** The following analysis sets will be used for planned analyses: Intent-to-treat, Safety, methods The primary hypothesis on EFS will be evaluated by comparing xevinapant with placebo in combination with CRT using a stratified log-rank test. The stratification factors are tumor size (T4 vs other) and lymph node involvement (N0-1 vs N2 vs N3). Hazard ratio will be estimated using a Cox-proportional hazard regression model adjusted for the randomization stratification factors. Treatment effect on other time-to-event endpoints will be estimated using Cox regression model adjusted for the randomization stratification factors. Estimation of the treatment effect on binary endpoints will be done using a logistic model adjusted for the randomization stratification factors. Descriptive statistics will be provided for safety endpoints. Hierarchical fixed sequence testing procedure is applied to control the type I error for the interim analysis and multiple hypotheses testing. The overall type I error is controlled at 0.025 one-sided. An O'Brien & Fleming type α spending is used for the calculation of the significance levels and efficacy boundaries (p-value scale). . the clinical study has about 90% power to detect the expected hazard ratio benefit. Safety and An IDMC will be established before the randomization of the first participant to provide safety and efficacy oversight efficacy during the study. The review of safety and efficacy data will be performed according to an IDMC Charter that will be oversight prepared before data collection start. All relevant data available from this study will be provided for these reviews. The responsibilities of the IDMC include: To minimize the exposure of participants to an unsafe therapy or dose. To make recommendations for changes in study processes where appropriate. To advise on the need for dose adjustments because of safety issues. To endorse continuation of the study.

[figure not shown]
It will also be the responsibility of the IDMC to review the efficacy results at the interim analysis.

At any time during the study when the IDMC recommends major changes, these recommendations will be presented to the Trial Steering Committee.

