The EFS follow-up period must be performed according to the planned visit schedule within the permitted visit windows. Participants without any progression, treatment failure, local or distant relapse, second cancers or death until Month 60 post-randomization, will enter the overall survival (OS) follow-up period after the Month 60 visit (FUP60). They will be followed for survival status only, at least every 3 months, until the End of Study (EOS) (see Section 7.2). Participants who progress according to RECIST v1.1, will enter the OS follow-up period at time of the event and will be followed up for survival status at least every 3 months, until the EOS (see Section 7.2).

In case of premature discontinuation of treatment in participants without disease progression (e.g., unacceptable toxicity), efficacy assessments will continue to be performed until an EFS event has been determined or Month 60 post-randomization, whichever occurs first.

During the EFS follow-up period and OS follow-up period, each study visit day and allowed time windows will be based on the randomization date.

After completion of the follow-up period, participants who have not discontinued the study prematurely will undergo the EOS assessments ([date of the 60 Month visit of the last on-study participant] ± 2 months) and will be considered as having completed the study (see Section 7.2 in case of premature withdrawal).

If the last on-study participant completes the OS follow-up (60 months after randomization), his/her EOS visit will be performed at the same time as his/her 60 Month visit. In case of premature discontinuation from the study, his/her EOS visit will be performed when he/she discontinues from the study.

The EOS visit can be performed by telephone call.

Table 1-1 Schedule of events / flow chart: screening & treatment period

Study Period		Scr		Combination therapy (CRT and Xevinapant/matched placebo) period															Monotherapy (xevinapant or matched placebo) period			
Cycles		-			1					2					3			4	5	6		
Visit Label		Scr	C1D1	C1D2	C1D4	C1D8	C1D15	C2D1	C2D2	C2D4	C2D8	C2D15	C3D1	C3D2	C3D4	C3D8	C3D15	C4D1	C5D1	C6D1	EOT	
Study Week	Section	(≤4 weeks)	1	1	1	2	3	4	4	4	5	6	7	7	7	8	9	10	13	16	20	
Study Visit Day (from 1st dose administration)		-28 to -1 (≤28 days)	1	2	4	8	15	22	23	25	29	36	43	44	46	50	57	64	85	106	134	
Cycle Visit Day		-	1	2	4	8	15	1	2	4	8	15	1	2	4	8	15	1	1	1	-	
Visit Window (days)		-	see foo	tnote 2	±12h			±3d		±12h			±3d		±12h			±3d	±3d	±3d	±7d	

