 - Participants without any progression, treatment failure, local or distant relapse, second cancers or death until Month 60 post-randomization, will enter the OS follow-up period after the visit of Month 60 (FUP60). They will be followed only for survival status, at least every 3 months until EOS (see also Section 7.2). Survival follow-up can be performed by telephone calls.
 - Note: At progression, the participant should complete EORTC QLQ-C30, EORTC QLQ-HN35 questionnaires
- 2. An audiometry is to be performed only if clinically indicated, as per institutional or national guidelines.
- 3. If the scan at EOT was negative (see Table 1-1 for schedule) no further ¹⁸F-FDG-PET scans should be performed. If the EOT scan was positive AND the participant underwent salvage surgery and END, no further ¹⁸F-FDG-PET scans should be performed. If EOT results were inconclusive AND the participant did not undergo salvage surgery and END, the ¹⁸F-FDG-PET scan should be repeated 12 weeks after EOT (Week 31±2weeks).
- 4. Response confirmation is not required.

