6.1.2.1.3. End of Xevinapant/Matched Placebo Treatment

Xevinapant/matched placebo treatment will be administered until the 6 cycles of therapy (i.e., 3 cycles of combination therapy followed by 3 cycles of monotherapy) are completed or until any of the study intervention discontinuation criteria described in Section 7.1 occur.

Note: If IMRT is permanently discontinued due to severe or intolerable toxicities as per Investigator's discretion, then the participant can enter the monotherapy period.

Discontinuation from study treatment does not mean discontinuation from the study. Procedures to be followed in the event of a study treatment discontinuation are presented in Section 7.1.

Procedures for discontinuation from study (not only study treatment) are described in Section 7.3.

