8.2. Efficacy Assessments

Assessment of tumor response to treatment will be assessed locally and centrally according to the Response Evaluation Criteria in Solid Tumors (RECIST v1.1) but will also take into consideration clinical, anatomopathological, and functional assessments of the tumor, as described in Appendix 13.5.

Tumor assessment and HRQL questionnaires or assessments should be continued until disease progression (as per RECIST v1.1) occurs or Month 60 post-randomization, whichever occurs first.

Participants who progress (as per RECIST v1.1) will enter the OS follow-up period at the time of the event and will be followed up for survival status at least every 3 months, until the EOS (see Section 7.2).

In case of premature discontinuation of treatment in participants without disease progression according to RECIST v1.1 (e.g., unacceptable toxicity), efficacy assessments will continue to be performed until an EFS event has been determined or Month 60 post-randomization, whichever occurs first.

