14.2.1 Overall Survival

Overall Survival (OS) time is defined as the time (in months) from randomization to death due to any cause.

$$OS = (date \ of \ death - randomization \ date +1) / 30.4375$$

Participants without documented death at the time of analysis will be censored at the date of last known contact.

The treatment difference in OS between the 2 treatment arms will be assessed using a one-sided stratified log-rank test as described for the primary analysis of EFS in Section 14.1.1. The significance boundaries are adjusted accordingly to control the family-wise error rate (FWER) at 2.5% one-sided (see also Table 3). The stratification factors are tumor size (T4 vs other) and lymph node involvement (N0-1 vs N2 vs N3).

The null and alternative hypotheses can be described in terms of hazard ratios as:

$$H_0^{OS}$$
: $\lambda_{(xevinapant + CRT)} / \lambda_{(placebo + CRT)} \ge 1$ versus

$$H_1^{OS}$$
: $\lambda_{(xevinapant + CRT)} / \lambda_{(placebo + CRT)} < 1$,

where $\lambda_{(xevinapant + CRT)}$, $\lambda_{(placebo + CRT)}$ represents the hazard of OS for the (xevinapant + CRT) and the (placebo + CRT) group respectively.

The treatment effect will be analyzed using a Cox Proportional Hazard model as described for the primary analysis of EFS in Section 14.1.1 including the RCI for the hazard ratio.

A further sensitivity analysis to address possible biases due to the dynamic allocation process will be performed based on permutation testing for the secondary endpoint OS as described for the primary endpoint EFS by BIRC in Section 14.1.2.

The Kaplan-Meier method (as described for the primary analysis of EFS in Section 14.1.1) will be used to estimate the OS in each treatment arm. Survival rates at 12, 24, 36, 48, and 60 months after randomization will be estimated with corresponding two-sided 95% CIs.

Graphical representation of the survival curves (Kaplan-Meier estimates) as step functions will be provided per treatment arm and per stratification variable.

The number and percentage of deaths will be presented by treatment arm. The OS time or censoring time will also be listed.

The same subgroup analyses as described for the EFS in Section 14.1.4 will be performed for OS.

Table 8: Estimand Attributes OS

Objective	Estimand Attributes
Secondary	
To demonstrate improvement in	Endpoint: OS defined as the time from date of randomization to death

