Overall Survival (OS) with xevinapant compared to placebo when added to chemoradiotherapy	Population: Patients with LA-SCCHN Stage III, IVA or IVB suitable for definitive CRT
	Treatment: Xevinapant and CRT followed by xevinapant followed by subsequent cancer therapy vs. placebo and CRT followed by placebo followed by subsequent cancer therapy
	Intercurrent Event Strategy: The endpoint will be analyzed regardless of whether or not the following intercurrent events had occurred (treatment-policy strategy):
	Treatment discontinuationStart of subsequent anticancer therapy
	Population-level Summary: Hazard ratio

Follow-up for OS

In order to assess the follow-up for OS, Kaplan-Meier estimates will be calculated using the censoring rules with reverse censoring indicator.

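### Protocol 7.3 lets the investigator withdraw a participant from the whole study for safety, behavioral or compliance reasons with no survival follow-up afterwards, in conflict with the rest of the protocol and the OS estimand

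*Protocol*

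**What the plan says.** Section 7.3 of the protocol covers premature withdrawal from the study at participant level. Treatment discontinuation has its own section, 7.1. Among the 7.3 triggers is "At the discretion of the Investigator for safety, behavioral, compliance, or administrative reasons", followed by examples in parentheses. The section asks for the reason to be recorded and, where possible, for end-of-study assessments before any further therapy.

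Withdrawal ends follow-up. The synopsis states: "Participants will be followed up until premature discontinuation from study" or until the last on-study participant reaches Month 60, and Section 4.1 has the same rule. Section 1.3 says, for the last on-study participant, that "his/her EOS visit will be performed when he/she discontinues from the study", and the end-of-study column of Table 1-3 also lists premature study discontinuation. No section asks for vital status or tumor assessment after an investigator-initiated withdrawal.

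The rules on stopping treatment go the other way. Section 6.1.2.1.3: "Discontinuation from study treatment does not mean discontinuation from the study". Section 8.2, for participants who stop treatment early without progression, with unacceptable toxicity as the example: "efficacy assessments will continue to be performed until an EFS event has been determined or Month 60 post-randomization, whichever occurs first".

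For OS, SAP 14.2.1 states: "The endpoint will be analyzed regardless of whether or not the following intercurrent events had occurred (treatment-policy strategy"). The events listed are treatment discontinuation and subsequent anticancer therapy. The censoring rule is: "Participants without documented death at the time of analysis will be censored at the date of last known contact".

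**The concern.** Safety, behavior and compliance may be reasons to stop treatment or to drop some visits. They are not reasons to stop asking whether the participant is alive, which the protocol makes easy: "Survival follow-up can be performed by telephone calls". A treatment-policy estimand for OS needs outcomes after treatment stops, and a withdrawn participant supplies none.

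Participants withdrawn for toxicity or non-compliance may well have a worse prognosis than those who stay, in which case censoring them is informative. Section 2.3.1 says CRT-related adverse events may be more frequent and more severe with xevinapant, so safety withdrawals could also be more common in that arm. The two together would move the observed OS and EFS hazard ratios in favor of xevinapant. EFS is the primary endpoint and OS the only secondary endpoint with confirmatory testing.

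The sponsor has already accepted the principle. The amendment history (Section 13.10, version 9.0) records that pregnancy was removed as a reason for study withdrawal because those participants should still be followed for OS.

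**Working it through.** **1. The same reason under different sections**

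| Section | Reason | Consequence |
|---|---|---|
| 7.1 | Unacceptable toxicity; investigator decision in the participant's interest | Treatment stops |
| 7.1 | Consent withdrawn for treatment only | Participant encouraged to stay for survival and efficacy follow-up |
| 6.1.2.1.2 | All treatments stopped, no EFS event | End-of-treatment visit, then EFS follow-up |
| 1.3, 8.2 | Early stop without progression, e.g. toxicity | Efficacy assessments to an EFS event or Month 60 |
| 7.3 | Safety, behavior, compliance, at investigator discretion | Study participation ends |

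A participant with unacceptable toxicity fits both 7.1 and 7.3, and nothing says which applies.

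**2. Can the analysis repair it?** Without an event, the withdrawn participant is censored at last adequate assessment for EFS (SAP Table 4, all three columns) or at last known contact for OS. Neither estimand table names study withdrawal. EFS Sensitivity #1 and #2 relax the new-therapy and missed-assessment rules, but they cannot use data that were never collected.

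**3. The plan's own figures.** With one-sided alpha 0.025, 1:1 allocation and a fixed design, power = Φ(√d/2 × |ln HR| − 1.96).

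- EFS: √429/2 × 0.3147 − 1.96 = 1.30, giving 90.3%. With the planned looks and the first-interim futility bound (HR 0.886) applied, 88.2%, as stated in SAP Table 3.
- OS: √386/2 × 0.2877 − 1.96 = 0.87, giving 80.7%. With the planned looks, 79.6%, as stated.

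**4. Planned loss.** Protocol 5.5 assumes 5% annual dropout in both arms. With 22-month accrual, mean follow-up is 33 months at month 44 and 54 months at month 65. Ignoring events, 1 − 0.95^2.75 = 13% (about 92 of 700) and 1 − 0.95^4.5 = 21% (about 144). The plan allows for the volume of loss, but not for loss that is informative or unequal by arm.

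**5. Size under assumptions.** Inputs from the documents: N = 700, 22-month accrual, 5% annual dropout; EFS control median 17 months and HR 0.73, read at month 44; OS HR 0.75 with control median 0.75 × 49.3 = 37 months, read at month 65. Inputs assumed, because the documents give none: withdrawals spread over months 0 to 6, the percentages below, and a hazard multiplied by k after withdrawal. Each cell gives the HR with follow-up kept, then the HR with withdrawals censored. Monte Carlo error is about 0.002 to 0.003.

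| Withdrawn, xevinapant vs placebo | k | EFS | OS |
|---|---|---|---|
| 5% vs 2% | 2 | 0.746, 0.731 (shift 0.015) | 0.765, 0.749 (shift 0.016) |
| 10% vs 5% | 2 | 0.757, 0.732 (shift 0.025) | 0.779, 0.751 (shift 0.028) |
| 10% vs 2% | 3 | 0.787, 0.729 (shift 0.058) | 0.815, 0.746 (shift 0.069) |

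With 5% in both arms and k from 1 to 3, the shift is at most about 0.005, and at these fixed dates about 19 to 28 EFS events and 17 to 28 deaths go unobserved. With k = 1 there is no bias in any split.

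The censored HR stays near its input value because censoring removes the excess risk after withdrawal. The treatment-policy effect includes that risk.

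**The case against.** The strongest reply is that 7.3 is not the route sites would take for toxicity. Sections 7.1, 6.1.2.1.2, 1.3 and 8.2 all direct such participants to stop treatment and stay in follow-up, and the examples in 7.3 are all operational: natural disaster, lost accreditation, a move abroad, staff leaving. It stands that nothing shows safety or compliance withdrawals to be common. It does not remove the conflict, because the sentence names safety, behavioral and compliance reasons separately from administrative ones.

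A reader might infer that the results will be biased toward xevinapant. The documents do not support that. They give no withdrawal rate, no arm difference and no hazard after withdrawal. Section 2.3.1 reports only a slight increase in dysphagia, mucositis and anemia on xevinapant in Phase 2, Section 4.3 reports similar numbers of grade 4 events, and the trial is double-blind. On the log scale, the OS shift at 5% versus 2% is ln(0.765/0.749) = 0.021, about a fifth of the standard error with 386 events (2/√386 = 0.102).

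A reader might also infer that confirmatory events are lost. The analyses are mainly event-driven (429 EFS events, 386 deaths, with a 60-month backstop for OS), so unobserved events mainly delay a cut-off. The counts in the working come from fixed dates.

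Nor would telephone contact alone rescue EFS. Under the primary rule and Sensitivity #1, a death after two or more missed assessments is censored at the last adequate one, so few primary EFS events would be recovered.

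Finally, the SAP tabulates study discontinuation by arm and primary reason (10.1.2) and EFS censoring reasons by arm (14.1.1). That would show an imbalance but not correct it.

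**Conclusion.** The point holds as a conflict between rules. Section 7.3 permits the investigator to end all follow-up for reasons that the rest of the protocol handles by stopping treatment alone, and it undercuts the treatment-policy estimand for OS. This is a stated rule, not a missing detail.

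The statistical consequence is conditional. Bias needs withdrawals that are both related to prognosis and unequal by arm. Under the assumed scenarios it is negligible when rates are equal, modest (0.015 to 0.03 on the hazard ratio) with unequal rates and a doubled hazard, and larger only in extreme cases such as 10% versus 2% with a tripled hazard. In that case OS would be 0.815 with follow-up kept, just outside the planned final boundary of 0.813, but would be observed as 0.746. That case shows the mechanism and is not a forecast. The planned power and event counts are unaffected. The change is worth making because it is cheap and protects both confirmatory endpoints.

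**What to change.** Reconcile 7.3 with 7.1, 6.1.2 and 8.2 so that safety, behavioral or compliance reasons alone do not end study follow-up. Follow-up ends only if the participant withdraws consent for it, is lost to follow-up or dies, if the study is terminated early under 7.4, or if contact is legally or practically impossible. Otherwise:

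- survival status continues to be sought by telephone or from records, which protects OS;
- scheduled tumor assessments continue where the participant agrees, which is what EFS needs.

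Leave decisions on stopping treatment to the existing rules.

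The cost is protocol wording, a letter to sites, survival contacts at least every 3 months, and continued assessments that are already on the schedule, for what should be a small number of participants.
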